9.6.3. Symptom Response Rate (SRR)

Symptom response rate (SRR) is defined as the proportion of subjects with $\geq 50\%$ reduction from baseline to the end of Cycle 6 in total symptom score (TSS) measured by MFSAF version 4.0. The SRR and 95% confidence interval will be provided. The TSS will be defined as the sum of each of the 7 symptom scores (Gwaltney, 2017). To allow indirect comparison with previous MF studies, a modified TSS (Mesa, 2013) will also be derived from the 6 symptoms considered (night sweats, pruritus, abdominal discomfort, early satiety, pain under ribs on left side, bone or muscle pain) and analysis of SRR will be also performed.

At each timepoint, the TSS (based on 7 symptoms) and the modified TSS will be calculated. Descriptive summary statistics (size, mean, standard deviation, median, range) will be provided for baseline scores, postbaseline scores and change from baseline for TSS, modified TSS and symptom scores.

Subjects without a baseline TSS > 0 will be considered non-evaluable (due to no place for symptom reduction) for the SRR analysis. Subjects with a missing TSS at the end of Cycle 6 or who had disease progression before the end of the Cycle 6 will be considered non-responders.

Details of the statistical analysis will be provided in a separate Health-related Quality of Life (HRQoL) SAP and will be reported under a separate cover.

9.6.4. Durability of Spleen Volume Response by MRI/CT (DR)

Durability of spleen volume response (DR) by MRI/CT is defined as time from the first documented spleen response (ie, $\geq 35\%$ reduction in spleen volume) to the date of subsequent progressive disease (PD) (ie, $\geq 25\%$ increase in spleen volume from baseline) or death, whichever is earlier. In the absence an event (ie, subsequent spleen volume reduction $< 35\%$ before the analysis is performed), the DR will be censored at the date of the last valid assessment performed before the analysis performed date.

Durability of spleen volume response by MRI/CT scan will be analyzed using Kaplan-Meier method. The K-M estimates of the 25th, 50th, and 75th percentiles and the 95% confidence interval of median will be provided, and the K-M curves will be plotted.

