2. STUDY OBJECTIVES AND ENDPOINTS

Table 1: Study Objectives

Primary Objective

The primary objective of the study is:
 
• To evaluate the percentage of subjects with at least 35% spleen volume reduction with fedratinib
Secondary Objective(s)

The secondary objectives are:
 
• To evaluate the safety of fedratinib• To evaluate the reduction of spleen size by palpation• To evaluate the symptom response rate in myelofibrosis (MF)-associated symptoms as measured by the Myelofibrosis Symptom Assessment Form (MFSAF) (Appendix B)• To evaluate the durability of spleen response by magnetic resonance imaging (MRI)/computer tomography (CT)-scan and by palpation• To evaluate the durability of symptoms response• To assess the effectiveness of the risk mitigation strategy for gastrointestinal events• To assess the effectiveness of the risk mitigation strategy for encephalopathy including Wernicke's

Table 2: Study Endpoints

Endpoint	Name	Description	Assessment Timeframe
Primary	Spleen volume response rate (RR)	Proportion of subjects who have a $\geq 35\%$ SVR at end of Cycle 6	From screening to the end of Cycle 6
Secondary	Safety profile of fedratinib	Incidence and severity of all Grade AEs per NCI CTCAE (Appendix E) Incidence and severity of Grade 3-4 AEs as per the NCI CTCAE (Appendix E), including laboratory parameters	From ICF signature up until 30 days post last dose For fedratinib related AEs, anytime until the last study visit
	Spleen response rate by palpation (RRP)	Proportion of subjects who have $\geq 50\%$ reduction in spleen size by palpation	From C1D1 to the end of Cycle 6
	Symptom response rate (SRR)	Proportion of subjects with $\geq 50\%$ reduction in total symptom scores measured by MFSAF	From C1D1 to the end of Cycle 6
	Durability of spleen volume response (DR)	Duration of $\geq 35\%$ SVR	From screening to the End of Treatment visit
	Durability of spleen response by palpation (DRP)	Duration of $\geq 50\%$ reduction in spleen size by palpation for subjects with a palpable spleen at least 5 cm below the left costal margin (LCM) at C1D1	From C1D1 until the 30-Day Follow-up after last dose visit
	Durability of symptoms response (DSR)	Duration of $\geq 50\%$ reduction in total symptom scores measured by MFSAF	From C1D1 until the 30-Day Follow-up after last dose visit

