6.3.2. Survival Follow-up

All subjects discontinued from protocol-prescribed therapy for any reason will be followed for survival, subsequent therapies, new malignancy and progression of myelofibrosis to acute myeloid leukemia (AML) every 3 months until death, up to 12 months after EOT, lost to follow-up, withdrawal of consent for further data collection, or study closure whichever comes first. See Section 10.7 for additional details on reporting.

A window of \pm 14 days is allowed for post treatment Survival Follow-up assessments; the visits should be performed every 3 months \pm 14 days and can be done by a documented telephone contact between site and subject.

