6.5. Response Assessment

Response assessments should occur at the end of C3, C6, C12, C18, C24, and EOT (and at the end of every 6th cycle [24 weeks]) as applicable afterwards. The response assessment can be combined with the Day 1 visit of the subsequent cycle or End of Treatment visit. The following assessments will be performed:

- **Symptoms response assessment:** Refer to Section 6.7.1
- **Spleen volume by MRI/CT scan:** Refer to Section 6.1
- **Spleen size by palpation:** Refer to Section 6.1

If a bone marrow assessment is performed as per standard of care, in addition to the assessments described above, the Investigator will assess response, for example, in terms of CR, PR, relapse, cytogenetic and molecular response as per IWG-MRT 2013 (Tefferi, 2013).

- [REDACTED]

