11.2. Study Discontinuation

Subjects who discontinue from treatment for any reason will be followed via telephone contact by the site for collection of data on survival including: cause(s) of death, disease progression, and posttreatment therapies for MPN-associated MF; until death, lost to follow up, or withdrawal of consent from the study.

Every attempt should be made to contact subjects during follow up unless subjects discontinue from the study. Every attempt should be made to collect all data on discontinued subjects.

The following events are considered sufficient reasons for discontinuing a subject from the study:

- Screen failure
 - The following information is to be captured in the subject's source documents and eCRF page(s): the date the informed consent forms (ICFs) were signed, demographics, prior ruxolitinib history, the reason a subject did not qualify for the

study, and the investigator's signature for the eCRF pages. Any adverse events experienced by a screen failure subject will be collected from the date of signing the ICF to the day the subject is confirmed as a screen failure. Serious adverse events occurring prior to treatment (after signing the ICF) are to be recorded within the eCRF, but do not require reporting to Celgene Drug Safety. Relevant information will also be recorded on the Screening Log.

- Withdrawal by subject
- Death
- Lost to follow-up
- Protocol deviation
- Study terminated by Sponsor
- Other (to be specified on the CRF)

The reason for study discontinuation should be recorded in the CRF and in the source documents.

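### Applied literally, section 9.6.4 counts deaths after the last scan as DR events but censors survivors back at that scan, which biases the Kaplan-Meier estimate downward; Table 2 implies a different rule and the two are not reconciled.

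*Combined protocol and SAP*

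**What the plan says.** Section 9.6.4 defines DR as the time from first documented response to subsequent PD (a spleen volume at least 25% above baseline) "or death, whichever is earlier". No limit is tied to last dose, last scan or new therapy. Without an event, "the DR will be censored at the date of the last valid assessment performed before the analysis performed date". The summary is by Kaplan-Meier: "Durability of spleen volume response by MRI/CT scan will be analyzed using Kaplan-Meier method", with quartiles and a 95% confidence interval for the median.

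Four other places bear on this:

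- **Scans (6.5 and Table 3).** "Response assessments should occur at the end of C3, C6, C12, C18, C24, and EOT", then every sixth cycle while treatment continues. None is scheduled after EOT.
- **Deaths.** Section 6.3.2 follows subjects off treatment "every 3 months until death, up to 12 months after EOT", by telephone if need be. Section 11.2 follows them "until death, lost to follow up, or withdrawal of consent from the study", with no 12-month limit.
- **Table 2.** The DR timeframe is "From screening to the End of Treatment visit", and DR is described as the duration of the 35% reduction, without mention of death.
- **The censoring sentence itself.** It begins "In the absence an event (ie, subsequent spleen volume reduction" and goes on to a reduction below 35%. That is loss of response, not PD or death.

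Section 9.6.5 gives durability by palpation (DRP) the same structure: death without limit, and censoring at the last valid assessment. Its Table 2 timeframe ends at the 30-Day Follow-up.

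**The concern.** Kaplan-Meier requires that whether and when a subject is censored carries no information about the later event. Take two responders with the same EOT date, both still in response on the EOT scan. One dies 11 months later: under 9.6.4 this is an event at EOT + 11 months, and that subject counts as at risk for all 11 months. The other is alive 12 months later and is censored back at the EOT scan. Follow-up beyond the scan is credited only to those who die. Deaths enter the numerator while the matching survivors are missing from the denominator, so the hazard is overstated.

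At stake is a stated secondary objective, reported as a median, quartiles and a curve. Planning figures in 9.3 (35% of 100 evaluable) imply about 35 responders, so a handful of such events matters.

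**Working it through.** **Stated design figure.** The documents give no figure for DR. The one design figure is power for the primary endpoint, and it reproduces: with 100 evaluable, the smallest count whose exact lower 95% bound exceeds 20% is 29, and the power at a true rate of 35% is 91.5% (stated: about 90%). Nothing below changes it.

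**Why the rule biases the curve.** Suppose a constant death rate L, treatment stopping at rate m independently of death, no PD, and F = 12 months of survival follow-up after EOT. For t up to F every death is recorded, so deaths at t occur at rate L·exp(−Lt). The literal rule removes from the risk set those who stopped at some s < t and will outlive s + F. Their share is

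exp(−LF) · [m/(L+m)] · (1 − exp(−(L+m)t)).

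The apparent hazard is therefore

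h(t) = L / {1 − exp(−L(F−t)) · [m/(L+m)] · (1 − exp(−(L+m)t))},

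which exceeds L for every t > 0. Example: true median 24 months gives L = ln 2/24 = 0.0289; mean treatment 12 months (section 3.2) gives m = 1/12 = 0.0833. At t = 12 the subtracted term is 0.743 × 0.740 = 0.549, so h = L/0.451, or 2.2 times the true hazard. Integrating h from 0 to 12 gives an apparent 12-month probability of 0.596 against a true 0.707.

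**Clean simulation** of the same setting, with 18 months' accrual plus 24 months (Protocol Summary) and 300,000 responders per case. It also gives 0.596 at 12 months. Medians in months:

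| True median | 9.6.4 literally | Deaths to EOT only, censor at last scan | All deaths, survivors at last known alive | Deaths to 30 days, censor at last scan |
|---|---|---|---|---|
| 12 | 9.6 | 12.0 | 12.0 | 11.1 |
| 24 | 14.8 | 24.0 | 24.0 | 22.2 |
| 36 | 19.3 | 35.9 | 35.9 | 32.6 |

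True 18-month probabilities of 0.354, 0.595 and 0.707 come out as 0.20, 0.41 and 0.53 under the literal rule. Both matched rules recover the truth. A 30-day death window with censoring at the EOT scan does not, because it keeps part of the mismatch.

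**Illustrative scenarios with PD.** Exponential times from first response, 12 months of survival follow-up, administrative cut at 21 to 39 months. All hazards are assumptions. Median DR in months:

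| Assumed medians (on-drug PD / other stops / survival after EOT) | Literal | Same events, survivors to last contact | Difference |
|---|---|---|---|
| 10.4 / 9 / 6 | 8.1 | 8.8 | 0.7 |
| 18 / 15 / 12 | 13.4 | 15.9 | 2.5 |

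Ending at EOT in the first scenario gives 10.4 months, the assumed on-drug PD median. That gap from 8.1 is not all bias: part of it is a change in what is being estimated.

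**Range check.** Eighteen further scenarios used the protocol scan schedule: mean treatment 9, 12 or 18 months; mean time to PD 20 or 40 months; median survival after EOT 6, 12 or 24 months. The literal rule gave a lower median than either matched rule in all 18. Responders whose event was solely a death after EOT made up 12% to 53%, about 4 to 18 of 35.

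**The case against.** The strongest reply is that Table 2 already ends DR at EOT. If it governs, later deaths are not events and the bias disappears. That stands, and it is why a reader should not infer that the DR estimate is certain to be biased. But Table 2 gives an assessment timeframe and no rule for deaths, while 9.6.4 is the analysis definition. Section 9.1 defers detail to a SAP, and no SAP text on DR is in the document supplied.

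Other points on that side also stand:

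- **Frequency of late deaths.** A reader might infer that they will be common from the 6-month median survival in section 1.1.4. That figure is for relapsed and refractory patients who stopped ruxolitinib, not fedratinib responders still in response, and exclusion criterion 26 removes subjects with a life expectancy under 6 months. Likewise the 10.4 months in section 1.2 is duration of response in previously untreated patients, pooled over two doses, not time to PD in this population. Both serve only as assumptions.
- **Net direction against Table 2's description.** Ending DR at PD rather than at loss of the 35% reduction lengthens it. So one cannot conclude that reported DR will understate how long the 35% reduction lasts; the two effects oppose each other.
- **Size against noise.** With about 35 responders, the simulated 95% sampling range for the first scenario's median is about 5.3 to 11.8 months, so 0.7 is well inside it. A systematic shift is still avoidable.
- **Choice of event.** The summary of changes shows that PD or death was adopted deliberately. The criticism is of the mismatched censoring, not of counting death.
- **Risk-set composition.** Subjects still on treatment and being scanned remain in the late risk sets, so these do not consist only of people who will die.

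**Conclusion.** The concern holds as a conflict in the text with a statistical consequence. If 9.6.4 is programmed as written, censoring depends on later survival and the Kaplan-Meier estimate of its own endpoint, PD or death, is too low. The direction follows from the rule and held throughout the range tried. The size is not known: 0.7 and 2.5 months are like-for-like differences under assumed hazards, and the true values could lie outside them. If Table 2 governs, this bias is absent, but 9.6.4 is then misstated and needs correcting anyway. Section 9.6.5 has the same structure. DR is a descriptive secondary endpoint with no test attached, so the primary endpoint and sample size are unaffected.

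**What to change.** 1. State one event definition in 9.6.4 and make the censoring sentence agree with it.
2. For the main DR analysis follow Table 2: count PD or death only up to the EOT visit, and before any subsequent MF therapy. Censor all other responders at the last valid scan within those limits. State what happens when the EOT scan is missed.
3. If all deaths are also of interest, report that as a supportive analysis with survivors censored at the date last known alive.
4. Apply the same matching to DRP in 9.6.5, with the 30-Day Follow-up as the end point for both deaths and censoring.
5. Reconcile the length of survival follow-up in 6.3.2 and 11.2.

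The cost is wording in 9.6.4, 9.6.5 and the SAP, plus one supportive table if item 3 is adopted. No new data are needed: subsequent therapies and survival are already collected under 6.3.2. The downside is fewer DR events and a somewhat wider confidence interval for the median.

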9.6.5. Durability of Spleen Response by Palpation (DRP)

Durability of spleen response by palpation (DRP) is defined as time from the date of first documented palpable spleen response, according to the IWG-MRT 2013 (Appendix D) to the date of subsequent PD according to the IWG-MRT 2013 or death, whichever is earlier.

Durability of spleen response by palpation according to the IWG-MRT 2013 criteria will be calculated for subjects that have an enlarged spleen at baseline (≥ 5 cm below LCM), and that have a spleen response by palpation. In the absence of an event (ie, no loss of spleen response by palpation) before the analysis is performed, the DRP will be censored at the date of the last valid assessment performed before the analysis performed date.

Durability of spleen response by palpation will be analyzed using Kaplan-Meier (K-M) method. The K-M estimates of the 25th, 50th, and 75th percentiles and the 95% confidence interval of median will be provided, and K-M curves will be plotted.

9.6.6. Durability of Symptoms Response (DSR)

Durability of symptoms response is defined as time from the first documented response in TSS (ie, reduction in TSS $\geq 50\%$) measured by MFSAF version 4.0 to the first documented TSS reduction $< 50\%$. In the absence of TSS reduction $< 50\%$ before the analysis performed, the DSR will be censored at the date of the last valid assessment performed before the analysis performed date. The DSR will be analyzed using K-M method. The K-M estimates of the 25th, 50th, and 75th percentiles and the 95% confidence intervals of median will be provided, and K-M curves will be plotted.

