6.7.1. Symptoms Response Assessment

The MF-related symptoms evaluation will be performed using the MFSAF v.4.0 version using a 7-day recall period (Gwaltney, 2017).

This questionnaire assesses 7 key MF-associated symptoms (night sweats, pruritus, abdominal discomfort, early satiety, pain under ribs on left side, bone or muscle pain, and fatigue). Due to the number of different questionnaires used in clinical trials for patient-reported MF symptoms, this version was developed following harmonization work conducted in collaboration with industry and the FDA with the aim to create a publicly available, consensus -based and

harmonized version of MF symptoms questionnaire ([Gwaltney, 2017](#)). The MFSAF version 4.0. was validated and recommended to be used in clinical trials to assess MF symptoms.

The Total Symptom Score is a composite score defined as the sum of each of the 7 symptom scores. To allow indirect comparison with previous MF studies, a modified Total Symptom Score ([Mesa, 2013](#)) will also be derived from the 6 symptoms considered (night sweats, pruritus, abdominal discomfort, early satiety, pain under ribs on left side, bone or muscle pain).

The MF-related symptoms evaluation will be performed at the site at screening, on Day 1 of each treatment cycle (and for Response Assessments), at the EOT and the 30-Day Follow-up after last dose visit. If exceptional circumstances preclude the continued administration of measures using planned modalities, then alternate administration methods may be required.

A copy of the questionnaire is presented in [Appendix B](#).

A large black rectangular box covers the majority of the page below the text, indicating that the questionnaire described in the text has been redacted.

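### Durability of symptom response censors responders who die while still in response, although both spleen durability endpoints count death as an event

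*Combined protocol and SAP*

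**What the plan says.** Section 9.6.6 defines DSR from the first documented TSS reduction of at least 50% "to the first documented TSS reduction" below 50%. If no such loss is recorded, "the DSR will be censored at the date of the last valid assessment performed before the analysis performed date". Neither death nor progression is listed as an event, and there is no separate rule for deaths.

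The two spleen durability endpoints are defined differently. Section 9.6.4 (MRI/CT) ends at progressive disease "or death, whichever is earlier". Section 9.6.5 (palpation) ends at "PD according to the IWG-MRT 2013 or death, whichever is earlier". The symptom response rate in section 9.6.3 treats subjects with a missing end-of-Cycle-6 TSS as non-responders, and likewise those "who had disease progression before the end of the Cycle 6 will be considered non-responders".

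Under section 6.7.1 the MFSAF is completed at screening, on Day 1 of each cycle, and "at the EOT and the 30-Day Follow-up after last dose visit". Survival is followed for up to 12 months after end of treatment (section 6.3.2), and no TSS is collected in that period. Section 9.6.3 adds: "Details of the statistical analysis will be provided in a separate Health-related Quality of Life (HRQoL) SAP". That SAP is not among the documents.

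**The concern.** Kaplan-Meier treats a censored responder as someone who could still lose the response later, at the same rate as those who remain under observation. That does not describe a subject who has died. Take a responder whose TSS response is first recorded at Cycle 4 Day 1, who is still in response at Cycle 8 Day 1, and who dies a week later. That subject contributes 4 × 28 = 112 days to DSR and then leaves the risk set without an event. In either spleen durability analysis, the same death would end the response.

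DSR is a named secondary endpoint (Table 2), and its Kaplan-Meier median would be reported alongside the two spleen medians. Section 1.1.4 describes a poor outlook after ruxolitinib, so deaths before recorded symptom loss are plausible. A reader who takes median DSR as the time patients live with symptom benefit would read it as longer than it is.

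The amendment summary that lists the statistical changes records that both spleen durability definitions were moved from loss of response to progression or death. It lists no such change for DSR, and no section explains why death should be handled differently there.

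**Working it through.** The plan states no figure for DSR, so there is none to reproduce. Its power statement (section 9.3) concerns the primary endpoint and does not bear on this point.

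**Step 1: how each endpoint treats the same subject.**

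| Subject in response at last assessment | DSR (9.6.6) | DR (9.6.4) | DRP (9.6.5) |
|---|---|---|---|
| Dies, no measured loss | Censored at last TSS | Event | Event |
| Progresses, TSS still reduced ≥50% | Stays at risk until the last TSS | Event | Event |
| Progresses, TSS loss recorded by the 30-Day Follow-up | Event at TSS loss | Event at progression | Event at progression |

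Only the first row is a problem in DSR. In the other two rows, symptom loss is still being measured.

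**Step 2: size under simple assumptions.** Inputs:

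- Median time to TSS loss, m = 10.4 months. This is the median duration of spleen response quoted in section 1.2 for the earlier Phase 3 study, borrowed here as an assumption. Values of 6 and 15 months were also tried.
- Annual risk of death or progression while in symptom response, p = 5 to 30%. This is an assumption; the documents give no value.
- Constant, independent hazards (assumption).

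Formulas: λ₁ = ln 2 / m; λ₂ = −ln(1 − p) / 12; median time alive, progression-free and in response = ln 2 / (λ₁ + λ₂). The current rule estimates m. The ratio is m / composite = 1 + λ₂/λ₁.

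For m = 10.4, λ₁ = 0.6931/10.4 = 0.0666 per month. For p = 20%, λ₂ = 0.2231/12 = 0.0186, so the composite median is 0.6931/0.0852 = 8.1 months and the ratio is 10.4/8.13 = 1.28.

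| Annual risk p | Composite median (m = 10.4) | Excess of current rule | Excess, m = 6 | Excess, m = 15 |
|---|---|---|---|---|
| 5% | 9.8 months | 6% | 4% | 9% |
| 10% | 9.2 | 13% | 8% | 19% |
| 20% | 8.1 | 28% | 16% | 40% |
| 30% | 7.2 | 45% | 26% | 64% |

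The risk p includes progression. Counting death alone means a smaller λ₂ and a smaller excess.

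**Step 3: does the direction hold in a trial of this size?** Trials were simulated with 26 responders (25.6% of 100, the symptom response rate quoted in section 1.2 for the earlier single-arm study), TSS every 28 days, 24 months of follow-up and annual risks of 10 to 30%. When TSS follow-up ran up to the death or progression, the median under the current rule was never the shorter one, and it was strictly longer in 46 to 100% of trials. Without a shared frailty the gaps ran from about 1 month (6.4 against 5.5) to about 6 months (15.6 against 9.2). With a shared frailty linking symptom loss to death or progression, the largest gap was about 10 months (20.2 against 10.5).

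**Step 4: what if the death comes long after the last TSS?** With m = 10.4 and the event dated some months after TSS collection stopped:

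| Gap from last TSS follow-up to event | Composite median (10 / 20 / 30% risk) | Current rule |
|---|---|---|
| 0 months | 9.2 / 8.3 / 7.4 | 11.0 |
| 3 | 10.1 / 9.2 / 8.3 | 11.0 |
| 6 | 10.1 / 10.1 / 9.6 | 11.0 |
| 12 | 12.0 / 12.1 / 12.9 | 11.0 |

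At a 12-month gap the direction reverses, because unobserved months are credited as response. Survival follow-up runs up to 12 months after end of treatment, so the case can arise.

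**The case against.** **Progression.** A reader might infer that DSR also censors subjects because they progress. It does not. TSS continues each cycle, at end of treatment and at the 30-Day Follow-up, and a loss recorded there is an event. A subject whose spleen has progressed but whose TSS is still reduced by at least 50% still has the symptom response. This objection stands, and the point is confined to death.

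**Bias or estimand.** A reader might also infer that the percentages above measure informative-censoring bias. They do not. Under the independent hazards used in Step 2, Kaplan-Meier correctly estimates time to symptom loss; the gap is between two different estimands. Dependence between worsening symptoms and death is plausible, but the documents give nothing from which to measure it. What remains is that section 9.6.6 never says it targets a duration that ignores death.

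**Comparability with the spleen endpoints.** DR and DRP end at progression or death, while DSR ends at the first single TSS reduction below 50%, with no confirmation. On its own measure DSR is therefore the stricter endpoint, and adding events to it would not put all three on one scale. The censoring text in 9.6.4 and 9.6.5 also describes loss of response as the event, at odds with their own definitions, and should be reconciled. This stands as an argument against simply copying the spleen definition. It does not explain why death ends a spleen response and not a symptom response.

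**Severity of the setting.** The 6-month median survival in section 1.1.4 refers to relapsed and refractory patients who stopped ruxolitinib, not to symptom responders on fedratinib, and exclusion criterion 26 removes subjects with a life expectancy under 6 months. The number of deaths in response could be small. This stands and limits the size.

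**Deferred detail.** The HRQoL SAP might add a rule for deaths. But 9.6.6 already fixes both the event and the censoring, so a different rule there would depart from the protocol.

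**Conclusion.** The point holds for death. As written, a responder who dies while in response is censored, so the DSR median describes time to symptom loss as if death did not occur, and it is longer than the time alive and in symptom response. The direction is clear when deaths fall close to the last TSS.

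The size cannot be derived from the documents. The 6 to 45% range rests on the borrowed 10.4-month median, an assumed 5 to 30% annual risk that includes progression, and constant independent hazards; a death-only figure would be lower. DSR is a descriptive secondary endpoint with no hypothesis test, so no formal conclusion of the trial depends on it. This is a cheap improvement to a reported estimate.

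**What to change.** In section 9.6.6, define DSR from first TSS response to the earlier of the first TSS reduction below 50% or death from any cause. Count a death as an event only if it falls within a prespecified window after the last valid TSS assessment; otherwise censor at that assessment. The sponsor should set the window before the data are analysed. Two cycle lengths (2 × 28 = 56 days) would be one option and lies well short of the 12-month gap at which the direction reversed.

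An acceptable alternative is to report the cumulative incidence of TSS loss with death as a competing event. Either way, keep the current rule as a supportive analysis, labelled as time to symptom loss with deaths censored. Progression need not be an event; if the sponsor wants it, add it as a sensitivity analysis.

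The cost is a wording change in the protocol and a matching one in the HRQoL SAP. Survival is already followed, so no new data are needed. The reported median DSR will usually be somewhat shorter.
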